#### 5.3.3 Exclusion Criteria

##### 5.3.3.1 General Exclusion Criteria

1. Individuals unable to make the decision to participate in a clinical investigation on their own.
2. Patient is currently programmed with segmented electrodes, and cannot tolerate omnidirectional programming.
3. Patient is being evaluated for a lead revision.

*This confidential document is the property of Abbott and shall not be reproduced, distributed, disclosed or used without the express written consent of Abbott*

## Clinical Investigation Plan

4. Patient has untreated clinically significant depression.
5. Patient has dementia that interferes with their ability to co-operate or comply with study requirements or comprehend the informed consent, as determined by the investigator.
6. Patient abuses drugs or alcohol.
7. Patient is currently enrolled or plans to enroll in another concurrent study that may confound the results of this clinical investigation.
8. Patient has a confirmation of diagnosis of a terminal illness associated with survival <12 months.
9. Presence of other anatomic or comorbid conditions, or other medical, social, or psychological conditions that, in the investigator's opinion, could limit the patient's ability to participate in the clinical study or to comply with follow-up requirements, or impact the scientific soundness of the clinical study results.
10. Pregnant or nursing patients and those who plan pregnancy during the clinical study follow-up period.

### 5.4 Subject Enrollment

A patient is considered enrolled in the clinical study from the moment the patient provides written informed consent and has been confirmed to meet all inclusion criteria and none of the exclusion criteria. Omnidirectional programming should be used from the time of enrollment to the Baseline visit.

### 5.5 Subject Withdrawal

Each enrolled subject shall remain in the clinical study until completion of the required follow-up period; however, a subject's participation in any clinical study is voluntary and the subject has the right to withdraw at any time without penalty or loss of benefit. Conceivable reasons for discontinuation may include, but not be limited to, the following:

- Subject death
- Subject voluntary withdrawal
- Subject lost-to follow-up as described below
- Subject's follow-up is terminated according to Section 3.3.
- Subject undergoes a DBS system revision or DBS system explant
- Subject does not meet the inclusion/exclusion criteria and does not require additional follow-up for safety reasons
- Subject's non-compliance
- Subject's participation is terminated by the PI or investigator, although the subject consented, since participation is no longer medically appropriate

The Sponsor must be notified of the reason(s) for subject discontinuation. The site will provide this information to the Sponsor. Investigators must also report this to their respective IRB as defined by their institution's procedure(s).

No additional follow-up will be required or data recorded from subjects once withdrawn from the clinical study. Subjects who withdraw will not be replaced by additional study subjects.

## Clinical Investigation Plan

Before the subject is withdrawn from the study, the site should make attempts to schedule the subject for a final clinical study visit. At this final follow-up visit, the subject will undergo the following assessments:

- Motor symptom evaluation (stimulation ON/medication ON) performed by a blinded assessor
- Quality of life assessment
- Medication (only PD or ET medications)- indicate the drug category the subject is currently taking on a long term basis, i.e. no short term medication

### Lost-to-Follow-up

If the subject misses two consecutive scheduled follow-up time points and the attempts at contacting the subject detailed below are unsuccessful, then the subject is considered lost-to-follow-up. Site personnel shall make all reasonable efforts to locate and communicate with the subject (and document these efforts in the source documents), including the following, at each contact time point:

- A minimum of two telephone calls on different days over the specified follow-up windows to contact the subject should be recorded in the source documentation, including date, time and initials of site personnel trying to make contact.
- If these attempts are unsuccessful, a certified letter should be sent to the subject.
- If a subject misses one or more non-consecutive follow-up contact time points, it will be considered a missed visit. The subject may then return for subsequent visits. If the subject misses two consecutive time points and the above-mentioned attempts at communicating with the subject are unsuccessful, the subject will be considered lost-to-follow-up.

**Note:** Telephone contact with general practitioner, non-clinical investigation neurologist or relative without the presence of the subject or indirect documentation obtained via discharge letters will not be considered as subject contact.

### **5.6 Total Expected Duration of the Clinical Study**

The total expected duration of the study is expected to be 24 months. Site activation and subject enrollment timelines can be difficult to predict, therefore the total duration of the study may end up being either shorter or longer than estimated.

### **5.7 Expected Duration of Each Subject's Participation**

The total expected duration of each subject's participation in the clinical study is approximately 6 months.

### **5.8 Number of Subjects**

Up to 40 subjects will be enrolled in the clinical study in order to analyze the primary endpoints.

### **5.9 Estimated Time Needed to Select Required Number of Subjects**

The expected duration of enrollment is approximately 18 months.

## Clinical Investigation Plan

### 6.0 TREATMENT AND EVALUATION OF ENDPOINTS

#### 6.1 Baseline

##### 6.1.1 Baseline Assessments

Subjects should have omnidirectional stimulation in use at the time of the Baseline visit. Informity should not be used. The following assessments and information will be collected at the Baseline visit:

- Demographics- subject's age and gender
- Disease history- subject's year of PD or ET symptom onset, year of initial PD or ET diagnosis, subject's impression of worst symptom (PD subjects only)
- Baseline programming- subject's current DBS programming parameters
- Therapeutic window of current parameter set
- TEED of current parameter set
- Duration of the most recent programming session preceding enrollment from the Clinician Programmer session logs (if available)
- Medication dosage (only PD or ET medications)- indicate the drug category the subject is currently taking on a long term basis, i.e. no short term medication
- Preoperative motor symptom evaluation (medication ON) from medical records (if available)
- Preoperative quality of life assessment from medical records (if available)
- DBS implant information
- Pre-op MRI and post-op CT images

An encrypted thumb drive containing de-identified MRI and CT images for all study subjects will be provided to sites and images will be sent to the Sponsor.

The following activities will be performed at the Baseline visit:

- Quality of life assessment
- Motor symptom evaluation (stimulation ON/medication ON) performed by a blinded assessor

The quality of life assessment must be performed prior to the motor symptom evaluation. Quality of life assessments will be performed using PDQ-39 for PD subjects, and QUEST for ET subjects (see Section 6.3.2). Quality of life assessment does not need to be collected if a patient was reprogrammed to omnidirectional stimulation on the same day as the Baseline visit. Motor symptom evaluation will be performed using UPDRS part III for PD subjects and Fahn-Tolosa-Marin tremor rating scale for ET subjects. For both evaluations, responses are rated on a 0 to 4-point scale where 0 indicates 'none' and 4 indicates 'severe' symptom. Motor symptom evaluation will be performed by a blinded assessor, who will not be aware of the subject's programming.

The Baseline visit can occur on the same day as the Enrollment visit, or on a separate day following the Enrollment visit. It should be ensured that the patient is programmed with omnidirectional stimulation upon enrollment. If the Baseline visit occurs on the same day, it is not necessary to collect quality of life measurements. The duration from the Enrollment visit to the Baseline visit must be less than or equal to 30 days.

## Clinical Investigation Plan

### 6.2 Informity Programming Procedure

#### 6.2.1 Procedures Involved in the Use of the Device Under Investigation

At the Informity Programming visit, the subject's Infinity DBS system will be programmed by a trained programmer (clinician or trained healthcare provider) using the Informity tool. The Clinician Programmer App IFU provides specific instructions for use of the Informity tool.

Subjects are to be instructed not to take their medication the night prior to or the morning of the Informity Programming visit; or depending on the type of medication the subject is taking (i.e. extended release or long acting) the investigator can use their clinical judgement to determine an adequate length of time that the subject should be off medication prior to the testing.

Using the Informity tool, multiple electrode contact configurations on each lead will be assessed by a programmer for therapeutic effects followed by assessment of side effects. The Best Segmented level (BSL) should be determined. Once the BSL has been determined, at a minimum, the three single segments at the BSL must be assessed. As the amplitude is increased by the programmer, the therapeutic effect on the motor symptoms will be based on the programmer's clinical judgement of partial and complete therapeutic benefit seen for the subject's primary motor symptoms. Once first therapeutic effect is determined, the programmer will test for transient and sustained side effects.

The width of the therapeutic window is defined as the electrical current at which a side effect appeared minus the electrical current at which complete therapeutic benefit was obtained. The TEED is defined as the total energy delivered by the system over an arbitrary period of time, and is determined from the programmed stimulation parameters and measured program impedance.

The programmer will review the results of the Informity tool to aid in selection of the electrode contact configuration that they will program the subject. The Balance Threshold or TW% ranking options must be evaluated in the decision process. The Informity Tool Programming Guidance document provides step-by-step instructions for using the Informity tool to select the electrode contact configuration. Subjects are expected to remain programmed with this configuration from the Informity Programming visit until the 3-month visit.

The programmer should use their clinical judgement to determine the amount of time required to rest between each electrode contact configuration evaluation. It is suggested to allow at least a 2-minute rest period between each electrode contact/segment tested. If desired by the subject or programmer, Informity Programming can be separated into two visits performed on back-to-back days in which the left-side or right-side DBS leads are separately programmed and evaluated (if the patient has bilateral DBS leads). If Informity Programming is performed over back-to-back days, then the programmer satisfaction survey is assessed on the second day.

The programmer who performs Informity tool programming must be different from the person who previously programmed that subject's DBS system.

The subject may be given a Patient Controller after the Informity Programming procedure, dependent on the clinician's recommendation for patient care.

The duration from the Baseline visit to the Informity Programming visit must be  $21 \pm 7$  days.

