## 4.0 ENDPOINTS

### 4.1 Primary Endpoints and Rationale

- 1) Change in therapeutic window size at the Informity programming visit compared to baseline
- 2) Change in TEED at the Informity programming visit compared to baseline

The primary endpoints were selected because it is hypothesized that they will be significantly improved following Infinity tool programming. Specifically, it is hypothesized that therapeutic window size will increase and TEED will decrease at the Informity programming visit compared to baseline.

*This confidential document is the property of Abbott and shall not be reproduced, distributed, disclosed or used without the express written consent of Abbott*

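### Primary endpoint 1 pairs two therapeutic windows that the CIP does not require to be obtained under the same conditions

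*Combined protocol and SAP*

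**What the plan says.** Section 4.1 of the CIP defines primary endpoint 1 as "Change in therapeutic window size at the Informity programming visit compared to baseline". Section 8.1.1 tests it with a paired t-test at 0.05, setting the configuration in use at baseline against the one in use after Informity programming.

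For the baseline value, Section 6.1.1 has one line, "Therapeutic window of current parameter set". It stands in the list of information to be collected, among items such as demographics, session-log duration and preoperative scores. Stimulation is to be omnidirectional, and "Informity should not be used". A separate list of activities performed at the visit contains "Motor symptom evaluation (stimulation ON/medication ON) performed by a blinded assessor".

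For the later value, Section 6.2.1 says "Subjects are to be instructed not to take their medication the night prior to or the morning of the Informity Programming visit", with an alternative that leaves the length of withholding to the investigator. Then "multiple electrode contact configurations on each lead will be assessed by a programmer", first for benefit and then for side effects, and "at a minimum, the three single segments at the BSL must be assessed". Benefit is the programmer's clinical judgement of the primary motor symptoms. The same section gives the formula: "The width of the therapeutic window is defined as the electrical current at which a side effect appeared", less the current that gave complete benefit. The programmer must not be someone who programmed that subject before. The two visits are 21 ± 7 days apart.

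**The concern.** A paired comparison isolates the change of interest only if both members of the pair are obtained in the same way. Here the later window has a described procedure, a named type of assessor and a medication instruction. The baseline window has none of these.

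The medication state is relevant on the CIP's own terms. The lower edge of the window is the current that gives complete benefit, judged on motor symptoms, and those are what the medication treats. Section 6.2.1 itself asks for an adequate time off medication before the testing.

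The study has a single arm, so no control group would show the same shift and allow it to be subtracted. Section 3.2 acknowledges possible bias from placebo response but does not mention unequal measurement of the windows. Its blinded assessor covers the motor evaluation, not the window. At stake is whether a wider (or unchanged) window can be attributed to the configuration chosen with the tool.

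**Working it through.** **1. The two measurements side by side**

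| Item | Baseline (6.1.1) | Informity visit (6.2.1) |
|---|---|---|
| Source | Not stated: new test or earlier record | New test |
| Procedure | Not stated; tool barred | Amplitude raised in the tool over several configurations |
| Assessor | Not stated | Programmer, different from any earlier programmer |
| Medication | Not stated for the window; ON for the motor evaluation | Withheld |
| Window formula | General formula in 6.2.1 can apply | Same formula |
| Side-effect threshold | Transient or sustained not stated | Same ambiguity |

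The last two rows do not separate the visits. The formula can serve both, and the threshold is open at both, although Section 4.3 records transient and sustained side effects separately. The first four rows are where the visits can differ.

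**2. What the t-test estimates**

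Let θ be the mean change due to configuration and b the mean change due to measurement conditions. The mean paired difference estimates θ + b. To isolate θ, both windows must be taken under the same conditions, or one configuration must be measured under both sets of conditions. The CIP requires neither. The stated minimum in the Informity session is the three single segments at the best segmented level, whereas baseline stimulation is omnidirectional (Sections 5.4 and 6.1.1). Retesting the baseline setting is possible but not required. Subjects whose baseline cathode was contact 2 or 3 (Section 8.3) may have it tested while that level is being found, which is only a partial check.

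**3. Illustration of consequence**

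The plan has no figure to reproduce: it gives no effect size, SD or power, and the number of subjects has no derivation. Inputs:

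- n = 40, the ceiling (Sections 3.0 and 5.8); n = 20 for one diagnosis, a subgroup and not the pooled primary test.
- α = 0.05 (Section 8.1.1), taken as two-sided because no sidedness is stated.
- One window value per subject: an assumption, since the CIP does not say how leads are combined.
- b in SDs of the paired difference: an assumption, range 0.1 to 0.5.

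With θ = 0, the probability of a significant wider window is 1 − F(t₀.₉₇₅,ₙ₋₁; n − 1, b√n), where F is the noncentral t distribution function. For n = 40 and b = 0.2, the noncentrality is 0.2 × √40 = 1.265 and the critical value is 2.023, which gives 23.4%.

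| b (SD) | n = 40 | n = 20 |
|---|---|---|
| 0 | 2.5% | 2.5% |
| 0.1 | 9.0% | 6.2% |
| 0.2 | 23.4% | 13.3% |
| 0.3 | 45.6% | 24.6% |
| 0.5 | 86.9% | 56.4% |

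This probability reaches 10% at b = 0.11 (n = 40) or 0.16 (n = 20), and 50% at 0.32 or 0.46.

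A shift the other way hides a real gain. With an assumed θ = 0.5 SD and b = 0, −0.2 and −0.3, power is 86.9%, 45.6% and 23.4% at n = 40, and 56.4%, 24.6% and 13.3% at n = 20. These figures would describe any biased paired t-test. They show sensitivity and do not estimate the bias in this study.

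**The case against.** The strongest reply is that silence is not a mismatch. Medication ON is attached only to the motor evaluation, in a different list from the window, so a reader who infers that the baseline window is taken on medication goes beyond the text. Sites could measure both windows off medication. The case report forms, the device instructions for use, the programming guidance and the separate SAP that Section 8.0 allows for were not available, and any of them could specify the baseline measurement. This stands, and it limits the point to what the CIP requires.

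It can also be said that barring the tool at baseline is the design, because the study contrasts tool-guided with earlier programming. The bar may refer only to programming, and the different-person rule is a deliberate bias control. This stands in part: absence of the tool does not by itself show that the window was measured differently. But Section 8.1.1 hypothesizes that the tool identifies better parameters and compares configurations. Unequal measurement is not part of that hypothesis, and no alternative baseline procedure is given.

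Finally, if the baseline window comes from earlier records, standardizing the visit would not cure the problem. That is correct, and it is why the source has to be stated first.

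**Conclusion.** The point holds as a gap in the CIP. Section 6.2.1 sets conditions for the second window, Section 6.1.1 sets none for the first, and the primary test pairs them. As written, the t-test cannot separate changed measurement conditions from changed configuration. This should be fixed. Confidence is medium: the CIP's silence is plain, but an actual mismatch is possible and not shown.

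The size and direction of any bias are unknown. The SD-shift figures rest on assumed shifts, one window per subject and a two-sided test. A reader might infer that the endpoint is biased towards success; the documents do not support a direction.

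A reader might also take the second primary endpoint, TEED, to be wholly unaffected. TEED is calculated from programmed parameters and impedance and is not measured by this window testing, but the amplitude chosen after testing off medication may still affect it. The documents do not settle whether it does.

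**What to change.** 1. Reconcile Sections 6.1.1 and 6.2.1. State that both windows are newly measured, in one medication state, by one amplitude-testing procedure, and against one named side-effect threshold (transient or sustained). Which medication state to use is for the sponsor to decide. The choice has to allow for Baseline falling on the day of enrollment and for the medication-ON motor evaluation at that visit.

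2. Preferably, also test the subject's baseline configuration in the Informity session, before the new configuration is selected. Use the tool where it can test that setting and a manual test otherwise. In Sections 4.1 and 8.1.1, make this within-session window the comparator for endpoint 1, and report the Baseline-visit window alongside as a sensitivity analysis.

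3. Log the time of this added test separately and exclude it from programming duration. Otherwise it would lengthen only the Informity side of the duration comparison in Section 8.1.2.

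Cost: a CIP amendment, because the comparator of a primary endpoint changes, and a few minutes per lead. As a rough guide, the suggested 2-minute rest plus the 2 minutes in Appendix II for a persistent side effect gives 2 + 2 = 4 minutes per lead, or 8 for two leads, plus amplitude-testing time that the CIP does not give. This is not a floor: the rest is only suggested, the other 2 minutes apply only to persistent effects, and a contact already tested adds little. Under step 2 the comparator would be judged by the unblinded Informity programmer, which should be reported as a limitation. Step 1 alone adds no visit but has the scheduling constraints named above.

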## Clinical Investigation Plan

### 3.2 Measures Taken to Avoid and Minimize Bias

There are several measures that will be taken in this study to minimize bias. First, the person who uses the Informity tool to program a patient in the study must be different from the person who programmed the settings used at baseline. Second, the motor symptom evaluation will be evaluated by a blinded assessor.

Since this study design is open-label and non-controlled, there is a possibility of bias from placebo response following programming with the Informity tool.

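### The Informity programmer judges both ends of the therapeutic window and is not kept from the recorded Baseline thresholds and window, so the readings could be anchored

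*Combined protocol and SAP*

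**What the plan says.** Section 4.1 names two primary endpoints: "Change in therapeutic window size at the Informity programming visit compared to baseline" and "Change in TEED at the Informity programming visit compared to baseline". It also gives the expected direction: "it is hypothesized that therapeutic window size will increase and TEED will decrease at the Informity programming visit compared to baseline".

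Section 6.2.1 defines the window as the side-effect current minus the complete-benefit current. On the lower end it says "the therapeutic effect on the motor symptoms will be based on the programmer's clinical judgement of partial and complete therapeutic benefit". On the upper end it says "Once first therapeutic effect is determined, the programmer will test for transient and sustained side effects". The same person then chooses what to program: "The programmer will review the results of the Informity tool to aid in selection of the electrode contact configuration". One of two ranking options has to be looked at, but its result is not said to bind. TEED is calculated from the programmed parameters and the measured impedance.

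The comparator comes first. Section 6.1.1 lists "Therapeutic window of current parameter set" and the matching TEED among the Baseline data, without saying who measures the window. Section 6.2.1 puts the Informity visit 21 ± 7 days later.

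Section 3.2 gives two protections. The Informity programmer "must be different from the person who programmed the settings used at baseline", and the motor symptom evaluation has a blinded assessor. It describes the study as open-label and uncontrolled, and the only bias it admits is placebo response.

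**The concern.** The window is a judged quantity at both ends. If the person judging has seen the Baseline currents and window, small unintended choices (calling complete benefit a step early, or a side effect a step late) all move the result the way the plan predicts.

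Such a shift is systematic. More subjects do not average it out, and in a single-arm study the paired t-test of Section 8.1.1 cannot tell it from an effect of the tool. The plan already accepts the principle for a secondary endpoint: in Sections 6.1.1 and 6.3.1 the motor assessor is kept unaware of the programming. The judged primary endpoint has no matching provision.

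**Working it through.** The plan gives no figure to reproduce. Section 5.8 sets a ceiling of 40 subjects, with no power, effect size or standard deviation. The check has two parts.

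**1. The sections set side by side**

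- *Does the comparator exist when the Informity thresholds are read?* Yes. It is collected at Baseline (6.1.1), and 21 − 7 = 14 to 21 + 7 = 28 days pass before the Informity visit (6.2.1).
- *Who reads the thresholds?* The programmer reads both, while controlling the amplitude (6.2.1).
- *Is the Baseline window withheld from that person?* No section says so.
- *Does the change of person achieve this?* No. It excludes whoever programmed the subject before (3.2, 6.2.1). It does not restrict access to the record.
- *Could the Informity programmer have measured the Baseline window?* Section 6.1.1 names no assessor. One might argue that measuring a window counts as programming, but neither 3.2 nor 6.2.1 says so.
- *Does the blinded assessor cover it?* No. That role is tied to the motor scores, which are secondary endpoints (4.2).

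**2. What a systematic shift would do to the test (illustration only)**

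Inputs from the plan: paired t-test, type-1 error 0.05 (8.1.1); n up to 40, and up to 20 per diagnosis (3.0). Assumptions: full enrolment with complete pairs, a two-sided test (sidedness is not stated), no true effect, normal differences, and a shift of b standard deviations of the paired difference. The values of b are not from the plan.

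P(significant and favourable) = 1 − F(t_crit; n − 1, b√n), where F is the noncentral t distribution function and t_crit is the 0.975 quantile: 2.023 for n=40 and 2.093 for n=20.

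| b | b√40 | n=40 | b√20 | n=20 |
|---|---|---|---|---|
| 0 | 0 | 2.5% | 0 | 2.5% |
| 0.1 | 0.63 | 9.0% | 0.45 | 6.2% |
| 0.2 | 1.26 | 23.4% | 0.89 | 13.3% |
| 0.3 | 1.90 | 45.6% | 1.34 | 24.6% |

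If the test is one-sided at 0.05 with n=40, the figures for b = 0, 0.1, 0.2 and 0.3 are 5.0%, 15.3%, 34.4% and 58.7%. The smallest observed mean shift that reaches two-sided significance is 2.023/√40 = 0.32 SD at n=40, and 2.093/√20 = 0.47 SD at n=20. The larger sample makes a given bias more likely to reach significance, not less.

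**The case against.** The strongest reply has four parts.

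*The programmer's discretion is limited.* Section 1.1.1 describes a standardised workflow. Section 6.2.1 sets a minimum of three segments to test and requires a ranking option to be considered. Appendix II defines partial and complete benefit, and separates transient from persistent side effects at 2 minutes. Section 6.2.1 also relies on a separate programming guidance document, which is not available here and might restrict access. This stands in part. These provisions add structure, so it would be wrong to say the endpoint has no safeguard. None of those in the plan is masking, and a safeguard for a primary endpoint belongs in Section 3.2.

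*Choosing well is the point of the tool.* Section 1.1.1 says the best configuration is the one with a wide window and low stimulation power. This stands fully. A reader might infer that selecting a wide-window, low-TEED configuration is itself bias. It is the intended use. Only a misjudged threshold is measurement bias.

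*TEED is calculated, not judged.* This also stands. A reader might infer that both primary endpoints are equally exposed, but judgement reaches TEED only through the settings programmed. Masking could not do much for it, because the current settings stay visible and, with an impedance, they are the inputs to Baseline TEED.

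*Expectation needs no Baseline number.* The direction is printed in the plan and the study is open-label, so a programmer could lean that way without seeing the record. This stands as a limit on the remedy. Withholding the values closes one route, and the plan offers nothing from which to judge that route's share.

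**Conclusion.** The point holds for the therapeutic window. One unmasked person judges both thresholds, the comparator is already on record, and nothing in the plan keeps it from that person or stops that person from having measured it.

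A reader might go further and infer that anchoring will occur, or that the 9% to 46% range estimates the plan's false-positive rate. The documents support neither. The range follows from assumed shifts of 0.1 to 0.3 SD with no true effect, against 2.5% with no shift. With no SD in the plan, these cannot be converted into milliamperes or tied to the part that masking would remove. The finding also rests on the CIP text alone; the guidance document and case report forms are kept separately.

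For a post-market study meant to characterise a marketed tool, this is an inexpensive improvement to consider, not a flaw that defeats the design.

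**What to change.** Add to Sections 3.2 and 6.2.1:

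- The Informity programmer does not take the Baseline window measurement.
- That person is not given the recorded Baseline threshold currents or window until all Informity threshold readings and the final configuration have been saved.
- Access to anything the investigator considers necessary for safe programming takes precedence, and such access is recorded.

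Add an item to the programming CRF on whether masking was kept. State in Section 3.2 that programmer expectation in an open-label study remains a possible bias for both primary endpoints.

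The cost is short text in two sections, one CRF item and the usual IRB handling of an amendment. No visits are added. No staff should be needed either: the person who programmed the baseline settings is already excluded from the Informity session and could take the Baseline window. Subjects already programmed cannot be masked in retrospect. The downside is that masking is partial: current settings stay visible and general expectation bias is not removed.
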